## STUDY SYNOPSIS

TITLE OF STUDY:	
Double blinded, randomized, Priorix®- and placebo-controlled trial to evaluate the optimal dose of MV-CHIK vaccine (against Chikungunya virus) in regard to immunogenicity, safety and tolerability in healthy volunteers	
STUDY CENTRE(S):	

 
– Department of Clinical Pharmacology, Medical University of Vienna (Austria)
 
– Hansa Sanatorium GmbH of Graz (Austria)
 
– Institute for specific Prophylaxis and Tropical Medicine, Vienna (Austria)
 
– Berlin Centre for Travel & Tropical Medicine, Berlin (Germany)
 
– Department of Tropical Medicine and Infectious Diseases, Rostock University Medical Center, Rostock (Germany)
 
– University Medical Centre Hamburg-Eppendorf, Bernhard Nocht Centre for Clinical Trials (BNCCT), Hamburg (Germany)
 
	
STUDY PERIOD:	PHASE OF DEVELOPMENT:
Start, August 2016	Phase 2
OBJECTIVES:	

 
• To investigate the immunogenicity and safety of MV-CHIK 28 days after primary immunization regimen, consisting of one or two vaccinations
 
• To investigate the immunogenicity, safety and tolerability of MV-CHIK booster dose 24 weeks after primary immunization
 
• To investigate the immunogenicity, safety and tolerability of MV-CHIK during the treatment period up to 28 days after the last treatment
 
• To identify dose and schedule of MV-CHIK to forward to Phase 3 clinical development
 
	
STUDY DESIGN:	

Double blinded, randomized, Priorix® and placebo-controlled dose finding, multi center phase 2 trial in 320 healthy volunteer subjects. (Priorix® is preferred as control vaccine, however in case of unavailability or shortness of supply also MMR-Vax-Pro® or an equal measles vaccine may be used as control-vaccine)
 
The subjects will be randomized to one of six treatment groups (A, B, C, D, M1 or M2).
 
Group A: MV-CHIK low dose/Priorix® on study day 0 and 28, placebo on day 196
 
Group B: placebo on study day 0 and MV-CHIK low dose/Priorix® on day 28 and boosting dose on day 196
	

Group C: MV-CHIK high dose/Priorix® on study day 0 and 28, placebo on day 196

Group D: placebo on study day 0 and MV-CHIK high dose/Priorix® on day 28 and boosting dose on day 196

Group M1: Priorix® on study day -28, MV-CHIK high dose on day 0 and 28 and placebo on day 168 and 196

Group M2: Priorix® on study day -28, placebo on day 0 and 28 and MV-CHIK high dose on day 168 and 196

All subjects of treatment group A, B, C and D will receive three i.m. injections (on study day 0, 28 and 196). Subjects of group A and B will receive MV-CHIK low dose or control vaccine Priorix® and subjects of group C and D will be treated with MV-CHIK high dose or the control-vaccine Priorix®. All subjects of group A, B, C and D additionally will be randomized to one of two treatment sequences: group A and C will receive MV-CHIK or control-vaccine on study day 0 and 28, followed by placebo (saline) on day 196, and group B and D receive placebo on study day 0 and MV-CHIK or Priorix® on day 28, followed by an additional vaccination of the same product on day 196 (boosting vaccination).

All subjects of the measles booster group M1 and M2 will receive five i.m. injections on study day -28, 0, 28, 168 and 196. The first vaccination will be Priorix® (or equivalent measles vaccine) on study day -28. Group M1 will receive MV-CHIK high dose vaccinations on day 0 and day 28 and placebo on day 168 and 196. Group M2 will receive placebo on day 0 and 28 and MV-CHIK high dose on day 168 and on day 196.

**NUMBER OF SUBJECTS (PLANNED AND ANALYSED):**

320 subjects

**DIAGNOSIS AND MAIN CRITERIA FOR INCLUSION:**

Healthy male or female volunteer subjects, 18 to 55 years old

**TEST PRODUCT, DOSE AND MODE OF ADMINISTRATION:**

MV-CHIK, a recombinant measles virus vaccine expressing Chikungunya virus antigens; powder for suspension for injection; concentration of low dose  $5 \times 10^4$  ( $\pm 0.5$  log) TCID50 per 0.3 mL or high dose  $5 \times 10^5$  ( $\pm 0.5$  log) TCID50 per 0.3 mL administered by i.m. injection.

**CONTROL TREATMENTS, DOSE AND MODE OF ADMINISTRATION:**

Control-vaccine: Priorix® or MMR-Vax-Pro® or equivalent measles vaccine, powder and solvent for suspension for injection of measles, mumps, and rubella vaccine (live). Administration by i.m injection of 0.5 mL after reconstitution in physiological saline solution 0.9%.

Placebo control: physiological saline solution 0.9%. Administration by i.m injection.

**DURATION OF STUDY:**

The estimated study duration per subject will be 33-37 weeks (~8 months). Women of childbearing potential will be followed up for additional 2 months to confirm no pregnancy

occurred within 3 months after the last vaccination. The overall study duration will take 3 years from study initiation until reporting.

**CRITERIA FOR EVALUATION:**

Primary end-point:

- Immunogenicity on day 56 confirmed by the presence of functional anti-chikungunya antibodies as determined by the plaque reduction neutralization test (PRNT50)

Secondary end-points:

- Immunogenicity on days 0, 28, 196 and 224; additionally, for group M1 and M2 on day -28 and 168 as confirmed by the presence of functional anti-chikungunya antibodies as determined by the plaque reduction neutralization test (PRNT50) and by ELISA.
- Measurement of anti-measles antibodies on days 0, 28 and 56; additionally, for group M1 and M2 on day -28 as determined by ELISA.
- Solicited local and systemic adverse events (AEs)
- Serious adverse events (SAEs)
- Rate of AEs during the 28 day post-vaccination period
- Safety laboratory parameters (hematology, serum chemistry, urinalysis)
- Shedding of live recombinant virus until day 196 (subset of subjects)
- Induction of a Chikungunya virus specific T cell response (subset of subjects)
- Pre-existing anti-vector immunity:
  - Immunogenicity of Chikungunya vaccine in the presence of recently boosted measles immunity (measles booster groups M1 and M2).
  - Relation of post-vaccination anti-chikungunya plaque reduction neutralization titers (PRNT50) and baseline anti-measles ELISA titers (all groups).

**STATISTICAL METHODS:**

The primary immunogenicity analysis will compare the PRNT50 antibody geometric mean titer (GMT) 28 days after one or two immunizations in the per-protocol (PP) analysis population between the treatment groups. GMTs and GMT ratios will be estimated by applying an analysis of variance including the factor vaccination group and adjusting for multiple comparisons according to Tukey-Kramer. This will be done using log-10 transformed data and taking the anti-log of the resulting point estimates the least squares means, least squares means differences and the corresponding 95% CIs.

All subjects entered into the study, who receive at least one vaccination, will be included in the safety analysis. For solicited local and solicited systemic AEs, the number and percentage of subjects with AEs will be summarized for the 7 day diary period, by AE grade (mild, moderate, severe), by group and by dose. Relatedness will not be assessed for solicited AEs.

For unsolicited AEs, the number and percentage of subjects with treatment emergent adverse events (AEs) and serious adverse events (SAEs) will be presented for each treatment group overall and by system organ class/preferred term, and by AE grade, and relatedness. For unsolicited AEs, all subjects will be included in the safety analysis based on the product received (“as treated”) for the time period summarized. Changes in laboratory values will be analyzed descriptively by grade and by group from study entry until time point of assessment.

#### Data Analysis:

A preliminary analysis including safety and immunogenicity data will be performed after all subjects completed Visit 3 (day 56). The goal of this analysis is to provide highly valuable data of the novel Chikungunya vaccine for further development. Results from this analysis will have no impact on the study design and treatment of the subjects in this study. A final analysis will be conducted once the last subject has completed the study.

#### Data Safety Monitoring Board:

An independent DSMB will be installed to periodically review accruing safety information, and if necessary, to determine whether study or individual subject stopping rules have been met. The DSMB will periodically review listings and summary tabulations of SAEs, deaths, solicited AEs, unsolicited AEs and AEs leading to withdrawal from further vaccination. After about 50% of subjects of treatment groups A, B, C and D completed Visit 3 (day 56), the DSMB will review safety and immunogenicity in order to evaluate the risk-benefit of the MV-CHIK administration and make recommendations to the sponsor regarding the further study conduct and/or protocol modifications, if needed. A written DSMB charter will be developed.

#### **BENEFIT/RISK ASSESSMENT:**

The measles virus vector is well known. Possible risks that are frequently associated with vaccination are the occurrence of local reactions e.g. edema, induration and erythema, transient local pain or tenderness at the injection site as well as mild to moderate headache, myalgia, arthralgia, flu-like symptoms or fatigue.

As any other vaccine, MV-CHIK might induce allergic and anaphylactic reactions, apart from the described local reactions at the vaccination site and systemic flu-like reactions. In rare cases the injection can lead to a vasovagal reaction immediately after injection of the vaccine. The needle pricks for blood sampling may also cause local reactions such as edema. The subjects cannot expect direct benefit from study participation, except for potential boosting of measles immunity and increasing immunity to CHIKV.

**LIST OF ABBREVIATIONS**

Ab	Antibody
Ag	Antigen
AE	Adverse event
AESI	AEs of Special Interest
ALT	Alanine aminotransferase (SGPT)
aPTT	Abbreviated partial thrombin time
AST	Aspartate aminotransferase (SGOT)
CCID 50	Cell culture infectious dose 50%
CHIKV	Chikungunya Virus
cm	Centimeter(s)
CRO	Contract research organization
dL	Deciliter(s)
DSMB	Data safety monitoring board
e.g.	For example
EC	Ethics committee
eCRF	Electronical case report form
EudraCT	European clinical trials database
ER	Emergency room
FDA	Food and drug administration
GCP	Good clinical practice
GMT	Geometric mean titer
HBV	Hepatitis B Virus
HCV	Hepatitis C Virus
HIV	Human immunodeficiency virus
i.e.	This is
i.m.	Intramuscularly
ICH	International conference on harmonization
IMP	Investigational medicinal product
IRB	Institutional review board
M1	Measles booster treatment group 1
M2	Measles booster treatment group 2
MedDRA	Medical dictionary for regulatory activities
mg	Milligram(s)
mL	Milliliter(s)
MV	Measles Virus
NA	Not assessable
NCR	Not clinically relevant
No.	Number(s)
PBMC	Peripheral blood mononuclear cells
PP	Per protocol
PRNT 50	Plaque reduction neutralization test 50%
SAE	Serious adverse event
SAR	Suspected adverse reaction
SCR	Seroconversion rate
SOP	Standard operating procedures
SUSAR	Suspected unexpected serious adverse reaction
TCID 50	Tissue culture infecting dose 50%
WHO	World health organization

## 1 TREATMENT GROUPS AND STUDY PLAN

### 1.1 Treatment groups

#### MV-CHIK vaccine:

Group A + B: low dose  $5 \times 10^4$  ( $\pm 0.5$  log) TCID50/ dose

Group C + D: high dose  $5 \times 10^5$  ( $\pm 0.5$  log) TCID50/ dose

Group M1 + M2: high dose  $5 \times 10^5$  ( $\pm 0.5$  log) TCID50/ dose

#### Control vaccine:

Priorix® or MMR-Vax-Pro® or equivalent measles, mumps rubella vaccine

#### Placebo injection:

Physiological saline solution 0.9%.

[figure not shown]
**Table 1 Treatment groups and vaccination schedule**

Group	Vaccine	Number of Subjects	Vaccine on day	Placebo on day
A	MV-CHIK low dose or	60	0 + 28	196
	control vaccine	10		
B	MV-CHIK low dose or	60	28 + 196	0
	control vaccine	10		
C	MV-CHIK high dose or	60	0 + 28	196
	control vaccine	10		
D	MV-CHIK high dose or	60	28 + 196	0
	control vaccine	10		
M1	control vaccine and	20	-28	168 + 196
	MV-CHIK high dose		0 + 28	
M2	control vaccine and	20	-28	0 + 28
	MV-CHIK high dose		168 + 196	
	Total Number of Subjects	320		

### 1.2 Clinical Study Plan

Subjects of group A and C will receive MV-CHIK or control-vaccine on day 0 and 28 and placebo (saline) on day 196. Subjects of group B and D will receive placebo (saline) on day 0, MV-CHIK or control-vaccine on day 28, followed by a booster of the same vaccine on day 196. Subjects randomized to measles booster group M1 or M2 will receive the control vaccine (Priorix® MMR-Vax-Pro® or equivalent measles vaccine) as first vaccination on day -28. Group M1 will then receive two MV-CHIK high dose vaccinations on day 0 and 28, followed by two placebo injections on day 168 and 196. Group M2 will receive two placebo injections on day 0 and 28, followed by two MV-CHIK high dose vaccinations on day 168 and 196.

Figure 1 Treatment Schedule

	V s	V0	V1	V2	V3	V4	V5	V6	(V7)
	-35	-28	0	28	56	168	198	224	286
screening / enrolment	randomi- zation								
	M1 + M2 1st shot	M1 + M2 2nd shot	M1 + M2 3rd shot			M1 + M2 4th shot	M1 + M2 5th shot		
	A+B+C+D V0 + V1 together on the same day 1st shot	A+B+C+ D 2nd shot					A+B+C+ D 3rd shot		

**A + B** = low dose or Priorix 
**C + D** = high dose or Priorix 
**M1 + M2** = Priorix and high dose 
placebo 
blood collection 

### 1.3 Visit procedures

**Table 2. Study Procedures**

Study Day	Screening Visit* Day -35*	Visit 0 Day -28	Visit 1 Day 0	Visit 2 Day 28	Visit 3 Day 56	Visit 4 Day 168	Visit 5 Day 196	Visit 6 Day 224	Visit 7 Day 286	Early Termination
Time windows / treatment groups	M1+M2: -35 to -29 A-D: -7 to -1	M1+M2: ±5 days **A-D -28 is study day 0	M1+M2 day 0 = V0+V1 at once on d 0	±5 days all groups	± 5 days all groups	±10 days only M1+M2	± 10 days all groups	± 10 days all groups	± 10 days all groups	
Informed consent	X									
Inclusion/exclusion criteria (1)	X	X	X (14)	X	X	X (14)	X			
HIV, hepatitis B/C, [blood: 8-10 mL]	X									
Demographic data	X									
Physical examination	X									
Vaccination history	X									
Hematology blood sample [3-5 mL] (6)	X				X			X		X
Coagulation parameter [blood: 3-5 mL] (7)	X				X			X		X
Clinical chemistry serum [8-10 mL] (8)	X				X			X		X
Urinalysis (10)	X				X			X		X
Medical history	X	X (2)								
Concomitant medications	X	X	X (14)	X	X	X (14)	X	X		X
Assessment of arthralgia	X	X	X (14)	X	X	X (14)	X	X		X
Symptom-directed physical exam (3)		X	X (14)	X	X	X (14)	X	X		X
Vital signs (4)	X	X	X (14)	X	X	X (14)	X	X		X
Urine pregnancy test (9)	X	X	X (14)	X	X	X (14)	X	X	(15)	X
Randomization		M1+M2 X	A B C D							
Study treatment: vaccination		X (14)	X	X		X (14)	X			
Immunogenicity 1: serum [blood: 2x 8-10 mL]		X (14)	X	X	X	X (14)	X	X		X
Immunogenicity 2 (5.1): [blood: 16-20 mL]		X (14)	X	X	X	X (14)	X	X		X
Measles antibody titer [no additional blood sample]		X (14)	X	X	X					X
T- cell analysis (5.2): [blood: 24-30 mL]			X	X	X	X (14)	X	X		X
Measles virus shedding (13): [blood: 2-3 mL, urine and saliva]			X (13)	X (13)			X (13)			
Local tolerability (12)		X (14)	X	X	X	X (14)	X	X		X
Dispense subject diary (11)		X (14)	X	X		X (14)	X			
Collect subject diary (11)			X (14)	X	X		X (14)	X		X
Adverse events		X (14,2)	X (2)	X	X	X (14)	X	X		X

\* Screening visit within 7 days before randomization

(1) After randomization only exclusion criteria, which could influence the subject's eligibility throughout the study will be checked. The following exclusion criteria are concerned: 1, 7, 8, 10, 19, 20, 21, 22 and 23

(2) Symptoms noted prior to randomization are not considered as adverse events but will be recorded as medical history

(3) Including system-based assessment if necessary according to symptom-directed physical examination. (section 11.2.2)

(4) Systolic and diastolic blood pressure, body temperature and pulse

(5.1) Sites outside of Vienna: serum samples (blood 2x 8-10 mL) to be collected for additional immunogenicity analyses (cross neutralization and passive transfer)

(5.2) Vienna sites only: PBMCs will be isolated from fresh blood (blood 24-30 mL and once at V3 48-60 mL). (section 8.3.2)

(6) Hemoglobin, hematocrit, erythrocyte count, differential white blood count, platelets (EDTA blood: 3-5 mL)

(7) Prothrombin time, aPTT, fibrinogen (blood: 3-5mL)

(8) Creatinine, sodium, potassium, calcium, aspartate aminotransferase (AST), alanine aminotransferase (ALT), alkaline phosphatase, bilirubin (blood 8-10 mL),

(9) Pregnancy test will be performed for women of childbearing potential. (section 8.3.6)

(10) Glucose, protein, pH, erythrocytes, leucocytes, nitrite, ketones, urobilinogen, bilirubin and specific gravity

(11) The subjects will assess local tolerability and systemic reactions themselves over a period of 7 consecutive days after each injection. (section 11.2.5)

(12) Investigation of injection site reaction 1 hour after vaccination and additionally before each subsequent vaccination. (section 11.2.4)

(13) Shedding: only in AKH Vienna, only in a subset of group A-D, on day 0, 28, 196 and additional shedding sampling visits on day 7, 10 and 14 (±1 day each) after the first vaccination on day 0. (section 8.3.1)

(14) Only measles booster group M1 and M2

(15) women of childbearing potential will be followed up by a phone call, to ensure no pregnancy occurred 3 months after the last vaccination

\*\* Group A, B, C, and D will perform Visit 0 and Visit 1 procedures on one day, group M1 and M2 will perform V0 and V1 on two days (28 days apart)

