17. History of severe adverse reactions to vaccine administration including anaphylaxis and related symptoms, such as urticaria, respiratory difficulty, angioedema and abdominal pain to vaccines, or history of allergic reaction likely to be exacerbated by any component of the vaccine or exacerbated by ingredients of the control vaccine (i.e. neomycin (sulfate), gelatin, sorbitol, mannitol, and sucrose)
18. History of anaphylaxis to drugs or major allergic reactions in general, which the investigator considers may compromise the safety of the volunteers
19. Clinically relevant abnormal laboratory values indicative of physical illness:
  - Hematology: hemoglobin, hematocrit, erythrocyte count, differential white blood count, platelets
  - Chemistry: creatinine (>1.7 mg/dL), potassium, sodium, calcium, AST/ALT  $\geq$  2.6 ULN, alkaline phosphatase, bilirubin
  - Coagulation parameter: prothrombin time (PT), activated partial thromboplastin time (aPTT), fibrinogen according to the evaluation of the principle investigator
  - Urinalysis according to the evaluation of the principle investigator
20. Use of medication during 2 weeks before the first vaccination and throughout the study, which the investigator considers may affect the validity of the study except hormonal

contraception in female subjects; prior to taking any medication during 72 h prior to the first vaccination, the study center should be consulted

21. Immunosuppressive drugs: use of corticosteroids (excluding topical preparations) or immunosuppressive drugs within 30 days prior to vaccination, or anticipated use during the trial
22. Receipt of blood products or immunoglobulins within 120 days prior to Screening Visit or anticipated receipt of any blood products or immunoglobulin during the trial
23. Pregnancy (positive pregnancy test at screening or during study phase), lactation or unreliable contraception in female subjects with child-bearing potential (for details please refer to section 8.3.6)
24. Subjects with any condition which in the opinion of the investigator makes the subject unsuitable for inclusion
25. Individuals who are living and/or working with severely immunocompromised people, children under 15 months old or pregnant women.
26. Inability or unwillingness to provide informed consent and to abide by the requirements of the study
27. Refusal to allow storage of specimens for future research.

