#### **7.4 Premature discontinuation**

Subjects have the right to withdraw consent to participation in the clinical study at any time for any reason without naming it.

It will be documented whether or not each subject completed the clinical trial. If, for a subject, trial treatment or observations have been discontinued, the reason will be recorded. Volunteers have to be withdrawn for the following reasons:

- voluntary subject withdrawal for any reason
- at the discretion of the investigator
- if an adverse event (including a concomitant illness) develops, which is considered by the investigator incompatible with the continuation of the study
- if the administration of a drug, which is not permitted by the exclusion criteria, is necessary
- subject failure to comply with the requirements of the protocol
- violation of exclusion criteria 1, 7, 8, 10, 19, 20, 21, 22 and 23 during the study

For any subject discontinuing the study before schedule, the investigator will:

- ask the subject to take part, as far as possible, in the early termination visit in order to examine the subject's health conditions and perform the required blood sampling for the clinical blood tests.
- complete the eCRF, indicating in the final visit, the date of termination, the date and time of the last dose administration and the reason for discontinuing the study
- arrange for alternative medical care for the withdrawn subject, if necessary.
- record in the eCRF any follow-up if the subject was withdrawn due to an AE.

All subjects who are discontinued prior to Visit 0 will be replaced.

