### **8.2 Treatment Procedures**

#### **8.2.1 Study day -28 ( $\pm 5$ days) /Visit 0 (or day 0 /Visit 1 for group A-D)**

Subjects, who do not have to be in a fasted state, are requested to return within 7 days after screening visit, at the study site where inclusion and exclusion criteria will be checked once again and their medical history and concomitant medication will be updated, if necessary. A urine pregnancy test will be performed in women of childbearing potential. Symptom-directed physical exam, system-based assessment (only if necessary according to symptom-directed physical exam) and vital signs (systolic and diastolic blood pressure, pulse and body temperature) will be recorded. In addition, the subjects will be asked if they experience any kind of arthralgia. Blood samples for baseline immunogenicity 1 and measles antibody titer will be drawn from an appropriate forearm or cubital vein. All study sites except the two sites in Vienna will collect serum samples for cross neutralization and passive transfer analyses (immunogenicity 2).

Then subjects will be randomized and will receive their 1st vaccination according to the assigned treatment group.

- Group A, B, C and D will perform Visit 0 = Visit 1 procedures on one day (study day 0, just one visit).
- Group M1 and M2 will perform Visit 0 and Visit 1 separated on two days, 28 days apart (study day -28 and study day 0, two visits)

All subjects will be observed for 1 hour after each vaccination before discharge from study site. One hour after vaccination local tolerability and adverse events, if applicable, will be recorded.

Subjects will be discharged after the dispense and the instructions for the use of the subject diaries took place (subjects are asked to report any adverse events in the diary for 7 days after vaccination). Only if the investigating physician considers the situation to be safe for the subjects, they will be allowed to leave the department and will be asked to return to study site after 28 days ( $\pm$  5 days).

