### **8.2.2 Study day 0 / Visit 1**

Subjects of the treatment groups A-D have performed these Visit 1 procedures together with Visit 0 on one day.

Subjects of group M1 and M2 will return to the site for this outpatient visit 28 ( $\pm$ 5 days) days after Visit 0. The inclusion/exclusion criteria and concomitant medication will be checked again. A symptom-directed physical exam, system-based assessment (only if necessary according to symptom-directed physical exam), assessment of arthralgia and evaluation of vital signs as well as body temperature will be recorded. Blood samples for immunogenicity 1 and measles antibody titer serum sample will be obtained and all study sites except the two sites in Vienna will collect serum samples for cross neutralization and passive transfer analyses (immunogenicity 2). From all subjects enrolled in Vienna blood samples will be

collected for T cell assays. A urine pregnancy test will be performed in women of childbearing potential. Subject diaries of group M1 and M2 will be collected and checked for completeness. Subjects of treatment group M1 and M2 will be assessed for local tolerability of the first vaccination and will then receive their 2nd injection. They will be observed for 1 hour after vaccination before discharge from study site. One hour after vaccination local tolerability and adverse events will be recorded, if applicable.

Subjects will be discharged after dispensing and explanation of the subject diaries, only if the investigating physician considers it to be safe for the subjects to leave the department and are asked to return to study site after 28 days ( $\pm$  5 days).

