### **8.2.3 Study day 28 ( $\pm$ 5 days) / Visit 2**

All subjects will return to the site for an outpatient visit 28 days ( $\pm$ 5 days) after Visit 1. The inclusion/exclusion criteria will be checked again. Blood samples for immunogenicity 1 and measles antibody titer serum sample will be obtained and all study sites except the two sites in Vienna will collect serum samples for cross neutralization and passive transfer analyses (immunogenicity 2). Symptom-directed physical exam, system-based assessment (only if necessary according to symptom-directed physical exam) and evaluation of vital signs as well as body temperature will be recorded. A urine pregnancy test will be performed in women of childbearing potential. Concomitant medication will be assessed. Subject diaries will be collected and checked for completeness.

Assessment of local tolerability of the previous injection site will take place. In addition, the subjects will be asked if they experience any kind of arthralgia.

All subjects will be vaccinated (groups A, B, C, D receive 2nd injection and group M1, M2 receive 3rd injection) and observed for 1 hour after vaccination before discharge from study site. One hour after vaccination local tolerability and adverse events, if applicable, will be recorded.

Subject diaries will be dispensed. The subjects are asked to report any adverse events in the diary for 7 days after vaccination. Adverse events and concomitant medication will be recorded, if applicable.

The subjects are asked to return to study site after 28 days for their next visit.

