## **20 DEVIATIONS FROM THE PROTOCOL**

### **20.1 Relevant Protocol Deviations**

Inclusion of subjects not satisfying the entry criteria will be subject to prior discussion with the sponsor and written approval from the sponsor. Subjects developing exclusion criteria during the study will be withdrawn; exceptions need prior discussion and written approval from the sponsor. All protocol deviations will be listed in the study report and assessed as to their influence on the quality of the study analysis. No deviations from the protocol of any type will be made without complying with all the IRB/Ethics Committee's established procedures in accordance with applicable regulations.

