1.5.3 Austria

	Screening Visit*	Visit 0	Visit 1	Visit 2	Visit 3	Visit 4	Visit 5	Visit 6	Early
Study Day	Day -35*	Day -28	Day 0	Day 28	Day 56	Day 168	Day 196	Day 224	Termination
Time windows / treatment groups	M1+M2: -35 to -29 A-D: -7 to -1	M1+M2: ±5 days **A-D -28 is study day 0	M1+M2 day 0 = V0+V1 at once on d	±5 days all groups	± 5 days all groups	±10 days only M1+M2	± 10 days all groups	± 10 days all groups	
Informed consent	X								
Inclusion/exclusion criteria (1)	X	X	X (14)	Х	X	X (14)	X		
HIV, hepatitis B/C, [blood: 8-10 mL]	X								
Demographic data	X								
Physical examination	X								
Vaccination history	X								
Hematology blood sample [3-5 mL] (6)	X				X			Х	X
Coagulation parameter [blood: 3-5 mL] (7)	X				X			X	X
Clinical chemistry serum [8-10 mL] (8)	X				X			Х	X
Urinalysis (10)	X				X			Х	X
Medical history	X	X (2)							
Concomitant medications	X	X	X (14)	Х	X	X (14)	X	Х	X
Assessment of arthralgia	X	X	X (14)	Х	X	X (14)	X	Х	X
Symptom-directed physical exam (3)		X	X (14)	Х	X	X (14)	X	X	X
Vital signs (4)	X	X	X (14)	Х	X	X (14)	X	Х	X
Urine pregnancy test (9)	X	X	X (14)	Х	X	X (14)	X	Х	X
Randomization	Ν	M1+M2 X A B	CD						
Study treatment: vaccination		X (14)	X	Х		X (14)	X		
Immunogenicity 1: serum [blood: 16-20 mL]		X (14)	X	Х	X	X (14)	X	X	X
Immunogenicity 2 (5.1): [blood: 16-20 mL]		X (14)	X	Х	X	X (14)	X	X	X
Measles antibody titer [no additional blood]		X (14)	X	Х	X				X
T- cell analysis (5.2): [blood: 24-30 mL]			X	Х	X	X (14)	X	Х	X
Measles virus shedding (13):			Y (12)	¥ (12)			Y (12)		
[blood: 2-3 mL, urine and saliva]			×(13)	X (13)			×(13)		
Local tolerability (12)		X (14)	X	Х	X	X (14)	X	Х	X
Dispense subject diary (11)		X (14)	X	Х		X (14)	X		
Collect subject diary (11)			X (14)	Х	X		X (14)	Х	X
Adverse events		X (14, 2)	X (2)	Х	X	X (14)	X	Х	X

Screening visit within 7 days before randomization

After randomization, only exclusion criteria which could influence the subject's eligibility throughout the study will be checked. The following exclusion criteria are concerned: 1, 7, 8, 10. 19, 20, 21, 22 and 23

(1) (2) Symptoms noted prior to randomization are not considered adverse events but will be recorded as medical history

Including system-based assessment if necessary according to symptom-directed physical examination. (section 11.2.2)

Systolic and diastolic blood pressure, body temperature and pulse

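### The post-randomisation eligibility check in Table 2 note (1) omits exclusion criterion 25 (vulnerable contacts), in conflict with protocol sections 20.1 and 8.2

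*Protocol*

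**What the plan says.** Note (1) belongs to the eligibility row of protocol Table 2 (section 1.3). It restricts the check after randomisation to criteria that can affect eligibility as the study goes on, and then names them: "The following exclusion criteria are concerned: 1, 7, 8, 10, 19, 20, 21, 22 and 23". Section 7.4 uses the same nine numbers as a ground for mandatory withdrawal: "violation of exclusion criteria 1, 7, 8, 10, 19, 20, 21, 22 and 23 during the study". The SAP flowcharts for Austria (1.5.3) and Germany (1.5.4) repeat the list.

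Criterion 25 in section 7.3 excludes "Individuals who are living and/or working with severely immunocompromised people, children under 15 months old or pregnant women". It is not among the nine.

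Two other parts of the protocol are worded without that limit:

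- Section 20.1: "Subjects developing exclusion criteria during the study will be withdrawn; exceptions need prior discussion and written approval from the sponsor".
- The later vaccination visits in section 8.2. Visit 1 for M1 and M2 (8.2.2) has "The inclusion/exclusion criteria and concomitant medication will be checked again", and Visit 2 (8.2.3) has "The inclusion/exclusion criteria will be checked again". Visits 4 and 5 (8.2.5 and 8.2.6) are worded in the same general way.

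The last check that is full on any reading is the one before randomisation (8.2.1), "where inclusion and exclusion criteria will be checked once again". It falls on Day 0 for groups A to D and Day -28 for M1 and M2.

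**The concern.** Criterion 25 protects other people, at home and at work, from exposure through someone given a live vaccine. A subject can come to meet it during the study by taking a new job, by a change in the household, when a contact becomes immunocompromised, or when a colleague or household member becomes pregnant. It therefore meets note (1)'s own test for staying on the list. The list does keep criterion 23, the subject's own pregnancy, but has nothing on a contact's.

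If a site works from note (1), nobody has to ask about contacts again. A later dose could then go to a person who would be turned away if screened that day. The consequences in 20.1 and 7.4 apply only once someone learns of the change.

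Shedding is itself still under study. Section 8.3.2 samples 30 to 50 subjects from groups A to D at one site. The last sample is at Day 196, and M1 and M2 are not sampled.

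**Working it through.** **Inputs.** Group sizes come from Table 1 and section 6.3, dose days from section 1.2, and the day of the full check from section 8.2.1. The plan states no dose count. Its one related figure, the total enrolment, reproduces: 4 × (60 + 10) + 20 + 20 = 320.

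**MV-CHIK doses.** (4 × 60 + 2 × 20) subjects × 2 doses = 560.

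**Time since the full check.** This is the nominal dose day minus the check day (0 for A to D, -28 for M1 and M2).

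| Days since check | MV-CHIK doses | Control doses | All live doses |
|---|---|---|---|
| 0 | A and C Day 0: 120 | A and C Day 0: 20; M1 and M2 Day -28: 40 | 180 |
| 28 | A to D Day 28: 240; M1 Day 0: 20 | A to D Day 28: 40 | 300 |
| 56 | M1 Day 28: 20 | none | 20 |
| 196 | B and D Day 196: 120; M2 Day 168: 20 | B and D Day 196: 20 | 160 |
| 224 | M2 Day 196: 20 | none | 20 |
| Total | 560 | 120 | 680 |

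**Results if note (1) governs.**

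- MV-CHIK doses after the full check: 560 − 120 = 440, and 440/560 = 79%.
- MV-CHIK doses at 28 to 56 days: 260 + 20 = 280, and 280/560 = 50%.
- MV-CHIK doses at 196 to 224 days: 140 + 20 = 160, and 160/560 = 29%.
- Live doses of either kind at 196 to 224 days: 160 + 20 = 180, and 180/680 = 26%. The control vaccine belongs in this count because it is also live.

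**Results if 8.2 is applied literally.** Every later vaccination visit includes a full check, so each of these counts is zero.

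**Injections at which the question would be asked.** Groups A to D: 280 × 2 = 560. M1 and M2: 40 × 4 = 160. Total: 720, made up of 440 MV-CHIK, 60 control vaccine and 220 placebo.

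**Do other provisions require anyone to ask?**

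- Section 20.1 and investigator discretion in 7.4 give a consequence, not a question.
- Section 11.3(c) concerns a medical condition of the subject, not of a contact.
- Section 8.3.6 requires two contraceptive methods, including condoms, and treats condoms as protection against passing on MV-CHIK. That is a real and continuing precaution, but it covers sexual partners and not colleagues or other household members.

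**The case against.** The strongest reply is that section 8.2 already orders a re-check at every later vaccination visit, without a limit, and that 20.1 with 7.4 supplies the consequence. On that view there is only an inconsistency between a table note and the visit text. Part of this stands: the dose counts depend on which text a site follows. It does not remove the point. Note (1) is attached to the very row that schedules the check, and 8.2 may be shorthand for that row. Nothing says which prevails.

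A reader might infer three stronger things that the documents do not support:

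- **That 29% is a risk.** It is a fact about the schedule. The documents give no rate at which subjects newly meet criterion 25, and the number of doses affected could be zero.
- **That 20.1 requires withdrawal in every case.** It allows exceptions with prior discussion and the sponsor's written approval.
- **That contacts are shown to be exposed.** No shedding or transmission from MV-CHIK is reported. The absence of a sample on any day after the 160 late doses means only that the planned sampling cannot inform on them.

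It can also be said that other criteria whose status may change, such as 2, 3, 14, 28 and 29, are off the list too. That is correct. Adding 25 alone leaves the mismatch with 20.1 for those. Finally, the consent pages were not available and may contain advice about contacts, so the point concerns the listed check only.

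**Conclusion.** The point holds as an omission and an internal conflict. Table 2 note (1), section 7.4 and both SAP flowcharts leave out criterion 25. Section 20.1 and the visit text in 8.2 do not share that limit, and no other provision clearly requires the question to be asked again.

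Its size, if note (1) governs, is 440 of 560 MV-CHIK doses after the last full check, including 160 that come 196 to 224 days after it. The counts assume full planned enrolment, no dropout and nominal days; Visits 4 and 5 have windows of ±10 days. The SAP's low dose for the Austrian M1 and M2 groups does not change them.

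This is worth correcting because the people protected are outside the trial and the remedy is one question. It is not evidence of harm, and it does not touch the immunogenicity results.

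**What to change.** 1. Add criterion 25 to the list in Table 2 note (1), in section 7.4 and in both SAP flowcharts.
2. Ask it of every subject before each later injection: Visit 1 for M1 and M2, Visit 2 for all, Visit 4 for M1 and M2, and Visit 5 for all. It must cover everyone because sites do not know who is due a live vaccine (section 6.4).
3. Have sections 8.2.2 to 8.2.6 refer to that list, so that only one reading remains.
4. Handle a subject who newly meets the criterion under the existing 20.1 rule: withdrawal, or an exception approved by the sponsor in writing. Stopping vaccination while keeping follow-up is a reasonable option, but it is the sponsor's choice and the correction does not depend on it.

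The cost is wording changes and one yes/no item within a check already scheduled: two per subject in A to D and four per subject in M1 and M2, 720 in all. A few subjects may miss a later dose and leave the per-protocol population (SAP 2.16). Having had at least one vaccination, they stay in the mITT and safety populations.
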